**Figure 1: Endartectomy Specimen Orientation and Process Map**

## 7 SAFETY MONITORING

The investigator will be responsible for study oversight, including monitoring safety, ensuring that the study is conducted according to the protocol and ensuring data integrity. The PI will review the data for safety concerns and data trends at regular intervals, and will promptly report to the IRB and NHLBI any Unanticipated Problem (UP), protocol deviation, or any other significant event that arises during the conduct of the study.

Safety monitoring for this study will focus on unanticipated problems involving risks to participants, including unanticipated problems that meet the definition of a serious adverse event.

### 7.1.1 *Unanticipated Problems*

The Office for Human Research Protections (OHRP) considers unanticipated problems involving risks to subjects or others to include, in general, any incident, experience, or outcome that meets **all** of the following criteria:

- unexpected in terms of nature, severity, or frequency given (a) the research procedures that are described in the protocol-related documents, such as the IRB-approved research protocol and informed consent document; and (b) the characteristics of the subject population being studied;
- related or possibly related to participation in the research (possibly related means there is a reasonable possibility that the incident, experience, or outcome may have been caused by the procedures involved in the research); and
- suggests that the research places subjects or others at a greater risk of harm (including physical, psychological, economic, or social harm) than was previously known or recognized.

### 7.1.2 *Serious Adverse Events*

A serious adverse event (SAE) is one that meets one or more of the following criteria:

- Results in death
- Is life-threatening (places the subject at immediate risk of death from the event as it occurred)
- Results in inpatient hospitalization or prolongation of existing hospitalization
- Results in a persistent or significant disability or incapacity
- Results in a congenital anomaly or birth defect

An important medical event that may not result in death, be life threatening, or require hospitalization may be considered an SAE when, based upon appropriate medical judgment, the event may jeopardize the subject and may require medical or surgical intervention to prevent one of the outcomes listed in this definition.

## 7.2 Reporting Procedures

Incidents or events that meet the OHRP criteria for unanticipated problems require the creation and completion of an unanticipated problem report form. OHRP recommends that investigators include the following information when reporting an adverse event, or any other incident, experience, or outcome as an unanticipated problem to the IRB:

- Appropriate identifying information for the research protocol, such as the title, investigator's name, and the IRB project number;
- A detailed description of the adverse event, incident, experience, or outcome;
- An explanation of the basis for determining that the adverse event, incident, experience, or outcome represents an unanticipated problem;
- A description of any changes to the protocol or other corrective actions that have been taken or are proposed in response to the unanticipated problem.
- Additional information required by the IRB as listed in Section 4.7 of the LSUHSC IRB Policies and Procedures Guidebook will also be provided in a timely manner.

To satisfy the requirement for prompt reporting, unanticipated problems will be reported using the following timeline:

- Unanticipated problems that are serious adverse events will be reported to the IRB and to NHLBI within 1 week of the investigator becoming aware of the event.
- Any other unanticipated problem will be reported to the IRB and to NHLBI within 2 weeks of the investigator becoming aware of the problem.
- All unanticipated problems should be reported to appropriate institutional officials (as required by an institution's written reporting procedures), the supporting agency head (or designee), and OHRP within one month of the IRB's receipt of the report of the problem from the investigator.

All unanticipated problems will be reported to NHLBI's centralized reporting system via Rho Product Safety:

- Product Safety Fax Line (US): [name]
- Product Safety Fax Line (International): [contact]
- Product Safety Email: [rho\\[contact]](mailto:[contact])

General questions about SAE reporting can be directed to the Rho Product Safety Help Line (available 8:00AM – 5:00PM Eastern Time):

- US: [name]
- International: [contact]

## 8 STATISTICAL ANALYSIS

A two-phase study is proposed. In the first phase, 75 surgical patients will be recruited as part of a training set; aims I-III will be evaluated with this set. In the second phase, at least 35 surgical patients will be recruited (possibly more, depending on the results of the first phase). Data from the second phase data will be used in the 510(k) application (i.e. Report of the results of the performance of the functional and structural analytes) and as additional training data for Aim III.

Two radiologists will be recruited for the study. The two radiologists will independently perform the manual contouring for all study patients, and one of these two radiologists will also perform the vascuCAP™ aided contouring after a sufficient wash-out period after the manual contouring and with appropriate blinding to their manual results.

### 8.1 Aim I

The first study aim is to estimate the bias and precision of each of the following functional analytes, which will be measured for each target lesion by both vascuCAP™ and histopathology:

- a. Plaque lipid
- b. Plaque fibrosis
- c. Plaque inflammation
- d. Intra-plaque hemorrhage burden and confidence.
- e. Plaque vascular leak
- f. Calcification

For each of these functional analytes, three measurements will be evaluated for a total of 18 measurements per target lesion: volume in mm^3, and degree and uniformity both measured on a three-point ordinal scale. The same measurements will be taken via histopathology, where the volume of each analyte will be measured using the same units (i.e. mm^3); however, degree and uniformity are graded subjectively on histopathology by the pathologist.

We anticipate that each patient will have at least one target lesion and some patients, especially the PAD patients, will have two target lesions, on average. There will be no replicate measurements (i.e. all of the measurements are obtained objectively by the algorithm so multiple runs should not produce different results).

For volume measurements for each analyte for each site (i.e. neck and leg), we will plot the value measured by histopathology vs. the difference between the value measured by vascuCAP™ and the value measured by histopathology. Any analyte not measurable will also be indicated on the plot using a different plotting character. The resulting plot will be inspected visually for the following:

1. Limits of vascuCAP™'s quantitation;
2. Associations between the magnitude of the histopathology measurement and bias; and
3. Associations between the magnitude of the histopathology measurements and heteroscedasticity in the vascuCAP™ measurements.

If the plots of carotid and femoral endarterectomies have similar distributions, then the data from these sites will be pooled; otherwise, separate analyses will be performed.

A linear model will be fit (for all of the data or for a subset of histopathology values, depending on the findings from the plot) where the dependent variable is the vascuCAP™ measurement ( $X$ ) and the independent variable is the histopathology value ( $Y$ ). Generalized estimating equations (GEEs) (to account for the fact that some patients will have more than one target lesion) will be used to estimate the linear function:  $E(Y|X) = \beta_0 + \beta_1 X$ . An unstructured working covariance will be used. We will construct a 95% CI for the intercept  $\beta_0$  using a t-statistic as the pivotal statistic. CIs not containing 0 indicate fixed bias. We will also construct a 95% CI for the slope  $\beta_1$ . CIs not containing 1 indicate proportional bias [11].

The precision of the vascuCAP™ measurements will be estimated by the standard deviation:

$$\sqrt{\frac{1}{n-1} \sum_{i=1}^n (Y_i - X_i - \bar{d})^2} \text{ where } \bar{d} \text{ is the sample mean of the differences, } \bar{d} = \frac{1}{n} \sum_{i=1}^n (Y_i - X_i) \text{ [1].}$$

We will construct a 95% CI for the precision using bootstrap methods.

We will plot the bias profile (plot of bias of measurements for various ranges of histopathology values vs. the histopathology value) and precision profile (plot of standard deviation of vascuCAP™ measurements from patients with similar histopathology values vs. the histopathology value) as visual summaries of vascuCAP™ performance for the bias and precision components, respectively [12].

In addition to reporting these technical performance characteristics of the volume measurements, we will also report i) the coverage probability (CP) and ii) a discrimination index [11]. The CP is the probability that the absolute difference between the value measured by vascuCAP™ and the value measured by histology is less than  $d_0$ , i.e.  $\pi = \Pr(|Y - X| < d_0)$ . We will plot the CP for a range of values for  $d_0$ . The discrimination ability of the measurements, i.e. the ability of vascuCAP™ to discriminate between different magnitudes of histopathology values, will be measured using the area under the ROC curve for continuous measures [13]. 95% CIs for the CP and ROC area will be constructed using methods for clustered binary data [14] and clustered ROC data [15], respectively.

The volume measurements are considered the most critical because they will be used to construct a score to predict rupture risk. Thus, we considered the width of 95% confidence intervals for the bias and the between-subject variance as a function of sample size (see Tables 1 and 2). The following assumptions were made: 1) the volume measurements are normally distributed; 2) carotid artery patients contribute one target lesion each, while PAD patients contribute two target lesions each; 3) target lesions from the same patient are moderately correlated ( $r=0.5$ ); 4) one-quarter of all patients will be PAD patients; 5) results from femoral and carotid target lesions can be pooled; 6) the average volume of an analyte is  $25\text{mm}^3$ ; and 6) the precision of the vascuCAP™ measurements is 10-20% of the volume of analyte.

From Table 4, if the SD was 15% of the mean volume, then we expect to be able to construct a 95% CI for the bias of total width of 10% with  $n=35$ . If the SD was 20%, then with  $n=35$  we expect to construct a 95% CI of total width of 14%. Similarly, from Table 5, if the SD was 15% of the mean volume, then with  $n=35$  we expect to be able to construct a 95% CI for the precision of total length 8%; if the SD was 20%, then we expect to be able to construct a 95% CI for the precision of total length 11%. We plan to recruit 75 patients (55 carotid artery patients and 20 PAD patients) in phase one to account for the fact that the estimates of bias and

precision may need to be reported in strata based on the magnitude of the histopathology volume and/or by anatomic location. In phase two we plan to recruit at least the minimum of 35 (25 carotid artery patients and 10 PAD patients) and possibly more depending on the results of the training set.

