### 3 OBJECTIVES

#### 3.1 Study Objectives

The vascuCAP™ measurements of structural and functional features of the arterial wall will be performed in patients undergoing endarterectomy for the following objectives:

Primary:

- I. Measure the bias, precision, and reproducibility of each of the functional analytes as measured by vascuCAP™ with respect to histopathologic results as ground truth, and assess their linear region and limits of quantitation.
- II. Establish performance characteristics of the structural and hemodynamic analytes, where an objective truth standard is lacking.

Secondary:

- III. Classify the target lesion according to whether the analytes suggest it is not a plaque, or if it is, which of the 8 AHA types best fits the analyte profile. Assess the accuracy of vascuCAP™'s classification against the histopathology classification.

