#### 3.2 Study Outcome Measures

Measured results will be compared in a blinded fashion with histology to assess performance of vascuCAP™-Profiling and build a prediction model in vascuCAP™-Scoring according to the following study endpoints:

- I. Measure the bias, precision, and reproducibility of each of the functional analytes as measured by vascuCAP™ with respect to histopathologic results as ground truth, and assess their linear region and limits of quantitation:
  - a. Plaque lipid core pool presence and volume.
  - b. Plaque fibrosis volume, degree, and uniformity.
  - c. Plaque inflammation burden, degree, and uniformity.
  - d. Intra-plaque hemorrhage burden and confidence.
  - e. Plaque vascular leak - volume, degree, and uniformity.
  - f. Calcification – volume, degree, and uniformity.
- II. Establish performance characteristics of the structural and hemodynamic analytes, where an objective truth standard is lacking:
  - a. Determine the interchangeability of structural measurements of wall thickness, remodeling ratio and luminal narrowing and hemodynamic measurements (ESS) with an imperfect (subjective) reference standard of manual contouring by radiologists. vascuCAP™ will be evaluated under two scenarios: fully-automated vascuCAP™, and a workflow where a reader will have the opportunity to review and adjust vascuCAP™ produced results.
  - b. Assess the reproducibility under different clinical sites, scanner models, and field strengths (dependent variable of interest being the interchangeability for each analyte relative to the imperfect reference standard) and with respect to ranges documented in literature according to collected co-variates.
- III. Classify the target lesion according to whether the analytes suggest it is not a plaque, or if it is, which of the 8 AHA types best fits the analyte profile. Assess the accuracy of vascuCAP™'s classification against the histopathology classification.

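### Section 8.1 gives the linear region, part of primary objective I, no named analysis or criterion, and its formal bias indicators cannot detect curvature roughly symmetric about the mean volume

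*Combined protocol and SAP*

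**What the plan says.** Section 3.1 makes it part of primary objective I to measure bias, precision and reproducibility "and assess their linear region and limits of quantitation". Section 3.2 repeats this as endpoint I: "with respect to histopathologic results as ground truth, and assess their linear region and limits of quantitation". The protocol summary says the same.

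Section 8.1 begins: "The first study aim is to estimate the bias and precision of each of the following functional analytes". For volumes it then provides:

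- a plot of the device-minus-histology difference against histology. "The resulting plot will be inspected visually for the following": limits of quantitation, "Associations between the magnitude of the histopathology measurement and bias", and heteroscedasticity.
- one regression: "A linear model will be fit (for all of the data or for a subset of histopathology values, depending on the findings from the plot". The text makes vascuCAP the dependent variable and says that "the independent variable is the histopathology value". The printed formula has the roles of X and Y the other way round.
- two bias indicators from that line: a 95% CI for the intercept compared with 0 (fixed bias), and one for the slope compared with 1, where "CIs not containing 1 indicate proportional bias".
- a bias profile by range of histology value, offered as a visual summary.
- a remark that bias and precision may need to be reported by volume stratum, given as one reason for recruiting 75 patients in phase one.

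Reproducibility by institution, scanner and field strength comes later in 8.1. The linear region is not mentioned anywhere in section 8.

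**The concern.** A straight-line fit takes linearity as given. Its intercept and slope can show that the line is in the wrong place, but not that a line is the wrong shape. If the device over-reads at both ends of the volume range and under-reads in the middle (or the reverse), the best line can still be the identity line, and both CIs will look as they do for a perfect device.

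The steps that could reveal such a shape are read by eye. The choice of subset for the fit is in effect an informal choice of linear range, made without a rule. Section 4 assigns the definitive 510(k) results to phase two. If the subset is chosen from the phase two plot, the reported intercept and slope are conditioned on that choice. Section 8.1 calls the volume measurements the most critical because they feed a rupture-risk score.

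**Working it through.** I write H for histology volume and D for the vascuCAP volume, because the plan uses X and Y inconsistently. The direction in the text (D on H) is used throughout.

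**Inputs from 8.1.** Mean volume 25 mm³; SD of differences 10%, 15% or 20% of that (2.5, 3.75, 5.0 mm³); normal volumes; one lesion per carotid patient and two per PAD patient; within-patient correlation 0.5; phase two minimum 35 patients (25 + 10); phase one 75 (55 + 20).

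**Assumptions not in the documents.** Between-lesion SD of true volume 8 mm³ for the table below (5 and 10 were also tried), and the shape and size of the curve.

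**Step 1: the plan's own figure.** m = 0.75 × 35 + 0.25 × 35 × 2/1.5 = 26.25 + 11.67 = 37.92. For SD 3.75 the half-width is t × 3.75/√37.92 = 1.234 mm³, so the total width is 2.468/25 = 9.9%. The plan states 10%, so it reproduces. This width concerns mean bias and says nothing about shape.

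**Step 2: why the line misses a symmetric curve.** Let k = (H − 25)/SD_H and bias g = A(k² − 1)/3. Then g = A at k = ±2 and −A/3 at k = 0. With A = 5 mm³ that is +20% of the mean volume at the extremes and −1.67 mm³ at the centre. Since E(k²) = 1, E(g) = 0. Cov(g, k) = A·E(k³)/3, which is 0 for any distribution symmetric about its mean. The population line is therefore exactly intercept 0, slope 1. The CI for overall mean bias is no help either: it contained 0 in about 95-96% of runs.

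**Step 3: simulation.** 2,000 to 4,000 runs per setting, normal volumes, least squares with patient-clustered robust SEs (working independence, where the plan specifies unstructured) and t-based CIs. Flagged means that the intercept CI excludes 0 or the slope CI excludes 1. The quadratic columns test an added H² term in the same model, without small-sample correction.

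| Patients | SD (mm³) | Straight device flagged | Curve (A = 5) flagged | Quadratic detects curve | Quadratic flags straight device |
|---|---|---|---|---|---|
| 35 | 2.5 | 8.5% | 12.1% | 98.9% | 10.5% |
| 35 | 3.75 | 8.6% | 11.4% | 91.4% | 10.0% |
| 35 | 5.0 | 8.9% | 11.5% | 76.6% | 10.8% |
| 75 | 2.5 | 7.8% | 9.7% | 100% | 9.1% |
| 75 | 3.75 | 8.0% | 9.5% | 99.6% | 9.3% |
| 75 | 5.0 | 7.8% | 8.2% | 97.1% | 8.6% |

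More patients do not help the existing indicators. A further set of clustered runs at 35 patients and SD 3.75 gave 8-13% flagged for the curve against 9-10% for a perfect device. There a small-sample-corrected quadratic term detected the curve in 81-92%.

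**Step 4: how far it depends on shape.** With right-skewed (lognormal) volumes E(k³) is not 0. The same form of curve (A = 5 or 7.5) then escapes in 58-70% of runs at 35 patients, so it is flagged in 30-42%; at 75 patients it escapes in 36-55% and is flagged in 45-64%. For one-sided saturation or floor effects at 35 patients, the existing indicators flag 64-86% and the corrected quadratic term only about 20%. A fall-off above the mean reaching −5 mm³ at +2 SD, with normal volumes, escapes in about 47% at 35 patients and 18-20% at 75.

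**The case against.** The plan is not blind to shape. The difference plot is inspected for bias that changes with magnitude, the fit may be restricted to a subset because of that plot, the bias profile shows bias by range, and phase one is sized with stratified reporting in mind. If the bias profile is made numerical in quintiles of histology volume (A = 5, normal volumes), at least one quintile CI excludes 0 in 52-82% of runs at 35 patients and 76-99% at 75, against about 25% for a straight device with no multiplicity control. A careful reader of the plots may well see the curve. This stands as evidence that the tools exist. It does not supply a criterion, or a rule for choosing the subset.

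The intercept and slope CIs are also labelled only as indicators of fixed and proportional bias, and symmetric curvature is neither. That stands. A reader might infer that a badly curved device would be cleared by an acceptance rule, but the plan contains no such rule.

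Nothing in the documents suggests that the device's error is symmetric, and for one-sided errors the existing indicators outperform a quadratic test. That stands too, so the quadratic term must be added to them and not replace them.

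Finally, extra testing has a price. At 10% false flags over six analytes, taken as independent, the chance of at least one is 1 − 0.9⁶ = 47%; at 5% it is 1 − 0.95⁶ = 26%. Significance alone should not decide.

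**Conclusion.** The point holds in a limited form. The linear region is a stated element of a primary objective, and section 8.1 gives it no named analysis, no criterion and no rule for fixing its bounds. The formal indicators miss curvature roughly symmetric about the mean volume: at 35 patients and SD 15%, 20% bias at the extremes is flagged in roughly 8-13% of trials against 9-10% for a perfect device. This rests on the plan's normality assumption, an assumed spread of true volumes, an assumed curve, use of all the data, and the regression direction in the text.

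Two stronger readings are not supported. One is that 8.1 redefines the aim as bias and precision only. That fits its opening sentence, but limits of quantitation and reproducibility reappear, and the subset fit is an informal step towards a linear range. The other is that any curved response escapes. Skewed volumes and one-sided departures are flagged far more often, so the gap is specific to roughly symmetric curves. This is a worthwhile, inexpensive improvement and does not show that the Aim I analysis is invalid.

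**What to change.** In 8.1, keep the intercept and slope CIs and add, for each volume analyte:

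1. A quadratic term in histology volume in the same patient-clustered model, with small-sample-corrected robust standard errors. Report its 95% CI.
2. The largest departure of the fitted curve from the line over the observed range, judged against an allowable deviation that the sponsor sets in advance, and not by significance alone.
3. Where the departure is material, bias with CI at fixed histology values read from the curve, alongside the intercept and slope.
4. A statement that the linear range is determined from phase one and fixed before phase two is analysed. It could be recorded when the product configuration is locked (section 4), so that the subset is not chosen on the definitive data.

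Cost: one more model term and one reporting rule per volume analyte, and no new data. With the correction about 5% of truly linear analytes would be flagged; without it, about 8-12% at 35 patients. The term adds little for one-sided saturation or floor effects, so the plots and existing indicators stay.

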### 6.3 Imaging Visit (Day 0-29)

- Subjects, meeting inclusion and exclusion criteria, will be contacted by research assistant or physician in person or by telephone to complete pre-MRI consent screening by use of the MRI safety checklist. After confirming consent to study protocol, those willing to participate will be scheduled to a 1-hour time-slot to appear at the Department of Radiology to undergo an MRI.
- At the appointed time, subjects will be met by a research assistant or physician and will be oriented. Consent will be confirmed both for the MR imaging as well as the pathology specimen (carotid endarterectomy specimen after surgery in carotid artery patients and peripheral arterial specimen in PAD patients) and the MRI safety checklist repeated. Subjects will change into hospital scrubs (provided) and remove any jewelry, watches, etc.
- The subject should be asked if he or she had a permanent coloring technique (i.e., tattooing) applied to any part of the body. This includes cosmetic applications such as eyeliner, lip-liner, lip coloring, as well as decorative designs.
- The subject should be informed of the risks associated with the site of the tattoo.
- The subject should be advised to immediately inform the MRI technologist regarding any unusual sensation felt at the site of the tattoo in association with the MR procedure.
- As a precautionary measure, a cold compress (e.g., ice bag) may be applied to the tattoo site during the MR procedure.
- Women of childbearing potential will be asked to provide a urine sample for a urine pregnancy test before each MRI study. If the test is negative, the patient may continue to participate. A positive pregnancy test will exclude further participation.
- Subjects will then be escorted by a research assistant/ physician into the MRI scan room and asked to lie on the imaging table. The patient will undergo MRI imaging of the specific arterial target, which is to include post-gadolinium contrast enhanced images. The total scan duration will be less than 60 minutes. All equipment for monitoring (ECG and respiration) and imaging is approved for human clinical use.

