**Table 3: Image acquisition sequences used in the protocol**

Contrast	T1	T2	TOF	Gadolinium	Diffusion	Phase Contrast
Imaging Sequence	BB 2D-TSE or FAST SE	T2 weighting 2D-TSE or FAST SE	MRA T1-FFE or FLASH or SPGR	DCE T1-TFE THRIVE or VIBE or FGRE	DWI SE-EPI	Q-flow T1-FFE or FLASH or SPGR
Acquisition	Before and after contrast inf; Fat Sat	Long TR, long TE; Fat Sat; inflow suppression	Fat Sat; inflow suppression	T1 weighted; Fat Sat	B values at 0, 500, and 1000 s/mm 	Choosing in phase and out of phase TEs

[figure not shown]
- **Carotid Artery.** All carotid MR axial image acquisitions will have a FOV of maximum 140×120mm, a slice thickness of maximum 4mm, and an acquisition matrix of at least 280×256, and a longitudinal coverage of at least 30mm. The MR imaging will be centered on the bifurcation of the symptomatic carotid arteries, defined as the arteries responsible for the neurological symptoms.
- **Femoral Artery:** The femoral artery will be scanned employing a standard leg coil placed around the thigh and conventional prospective ECG triggering. All femoral MR axial image acquisitions will have a FOV of maximum 140×120mm, a slice thickness of maximum 4mm, and an acquisition matrix of at least 280×256, and a longitudinal coverage of at least 15 cm. The MR imaging will start at the femoral bifurcation and continuing through the adductor canal.

Gadolinium intravenous injection (0.1mmol/kg) will take place in between the MRI scans while the subject is lying in the scanner. A physician will be present at all times. During the imaging procedure, subjects will be monitored physiologically by the ECG and respiration monitoring devices, and also observed by closed circuit television. Further, they will have an attached emergency call button in-hand to activate voice communication. Following completion of the imaging study, subjects will be excused and their participation in the study complete.

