**Table 5: Estimated 95% CIs for SD Based on Total Sample Size (n)\***

	n=10	n=20	n=30	n=40	n=50	n=60
SD=2.5	[1.80,4.77]	[1.98,3.81]	[2.08,3.51]	[2.11,3.29]	[2.16,3.20]	[2.19,3.14]
SD=3.75	[2.70,7.16]	[2.97,5.71]	[3.11,5.26]	[3.17,4.94]	[3.24,4.80]	[3.29,4.71]
SD=5.0	[3.60,9.54]	[3.96,7.61]	[4.15,7.02]	[4.22,6.59]	[4.31,6.40]	[4.38,6.29]

\*The effective sample size,  $m$ , is calculated as  $m=(3/4)n+(1/4)n(2/[1+(s-1)0.5])$ , where  $s=2$ .

Then the 95% CI for the SD is  $[\sqrt{\frac{(m-1)s^2}{\chi_{\frac{\alpha}{2},(m-1)}^2}}, \sqrt{\frac{(m-1)s^2}{\chi_{(1-\frac{\alpha}{2}), (m-1)}^2}}]$ .

For degree and uniformity measurements for each analyte for each site (i.e. neck and leg), we will tabulate the histopathology value vs. the vascuCAP™ value. Any analyte not measurable will also be indicated in the table. In the distributions in the tables are similar, then the data from the two sites will be pooled.

The coverage probability (CP) will be reported which is the probability that the absolute difference between the value measured by vascuCAP™ and the value measured by histology is less than  $d_0$ , i.e.  $\pi = \Pr(|Y - X| < d_0)$ . We will report the CP for values for  $d_0$  of 0 and 1. 95% CIs for the CP will be constructed using methods for clustered binary data [6].

For volume, degree, and uniformity of the six functional analytes, we will estimate the reproducibility of the measures at different institutions (two sites), and under different scanner models and field strengths (1.5 and 3.0) and with respect to ranges documented in the literature according to collected patient characteristics. Multiple variable linear and logistic regression models will be built, where the dependent variable is the difference between the measured functional analyte and the true value, and the independent variables are institution, scanner model, field strengths, and patient characteristics. We will test whether the independent variables in the model are predictors of bias using F-tests, and Wald tests, respectively.

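### For Aim I volumes, the reproducibility analysis tests only for a shift in mean bias by site, scanner or field strength; extra scatter on one scanner would usually go unflagged, and scan-rescan variation cannot be estimated

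*Combined protocol and SAP*

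**What the plan says.** Section 3.1 sets primary objective I as "Measure the bias, precision, and reproducibility of each of the functional analytes as measured by vascuCAP™", with histopathology as the reference. The Protocol Summary and section 3.2 repeat it. Section 8.1 opens more narrowly: "The first study aim is to estimate the bias and precision of each of the following functional analytes".

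On imaging, section 6.3 schedules one visit: "those willing to participate will be scheduled to a 1-hour time-slot to appear at the Department of Radiology to undergo an MRI". It ends with "Following completion of the imaging study, subjects will be excused and their participation in the study complete". No second scan is scheduled.

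On replicates, section 8.1 says "There will be no replicate measurements (i.e. all of the measurements are obtained objectively by the algorithm", and infers from this that repeated runs would agree.

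The reproducibility paragraph closes section 8.1, after Table 5. It regresses the difference between vascuCAP and histology on institution (two sites), scanner model, field strength (1.5 and 3.0) and patient characteristics. The test is then: "We will test whether the independent variables in the model are predictors of bias using F-tests, and Wald tests, respectively".

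Precision is handled earlier in 8.1 as the SD of the vascuCAP-histology differences, with a bootstrap CI and a profile against the histology value. The strata foreseen for bias and precision are histology volume and anatomic location, not site or scanner. No within-subject SD, reproducibility coefficient, acceptance limit, significance level or sample size is given for reproducibility.

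**The concern.** A deterministic algorithm gives the same output from the same images. Variation from repositioning, contrast timing, motion, scanner and field strength enters when the images are acquired. With one imaging visit per patient, that variation is part of the overall SD against histology and cannot be separated from it. Every comparison of sites, scanners or field strengths is also between different patients.

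For volumes, which section 8.1 treats as the most critical measurements, the planned regression asks whether a factor moves the average difference. It does not ask whether a factor changes the spread. A device can have the same mean bias on two scanners and be much less precise on one of them. Phase-two data are to support the 510(k) performance results for the functional analytes, so what the reproducibility analysis can and cannot show should be clear before those data are analysed.

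**Working it through.** **1. The plan's own figures.** The only sizing in 8.1 concerns bias and overall SD. At n = 35 the effective sample size is m = (3/4)(35) + (1/4)(35)(2/1.5) = 26.25 + 11.67 = 37.92.

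- *Bias.* With SD 3.75 mm³ and t on 34 df, the half-width is 2.032 × 3.75/√37.92 = 1.24 mm³. The total width is 2.48/25 = 9.9% (stated 10%). With SD 5.0 it is 13.2% (stated 14%).
- *Precision.* The total widths are 7.8% and 10.4% (stated 8% and 11%), using m − 1 in the numerator and chi-square on n − 1 df. With m − 1 df throughout, as the Table 5 footnote has it, they are 7.2% and 9.6%.

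The stated widths are therefore reproduced closely. None of them concerns reproducibility.

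**2. What one scan cannot show.** Total variance = scan-to-scan variance + all other variance. A total SD of 3.75 mm³ fits either of these:

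| Scan-to-scan SD (mm³) | Other SD (mm³) | Repeatability coefficient, 2.77 × scan-to-scan SD (mm³) |
|---|---|---|
| 0.5 | √(3.75² − 0.5²) = 3.72 | 1.4 |
| 3.5 | √(3.75² − 3.5²) = 1.35 | 9.7 |

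The planned data cannot tell these apart.

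**3. Why the mean test misses scatter.** Take two scanners with equal mean bias and SDs of 2.5 and 5.0 mm³, and one lesion per patient. The pooled test uses variance s²(1/n₁ + 1/n₂), while the true variance of the difference in means is 2.5²/n₁ + 5²/n₂.

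- *18/17.* s² = (17 × 6.25 + 16 × 25)/33 = 15.34. Variance used: 15.34 × 0.1144 = 1.75. True: 0.35 + 1.47 = 1.82. These are nearly equal, so the test rejects at about its nominal level (5.7% simulated).
- *25/10, noisier scanner on 10.* s² = (24 × 6.25 + 9 × 25)/33 = 11.36. Used: 11.36 × 0.14 = 1.59. True: 0.25 + 2.50 = 2.75. The test over-rejects (13.4%).
- *10/25, noisier scanner on 25.* s² = (9 × 6.25 + 24 × 25)/33 = 19.89. Used: 19.89 × 0.14 = 2.78. True: 0.625 + 1.00 = 1.625. The test under-rejects (1.2%).

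The departures from 5% come from the unequal split. They do not show useful sensitivity to scatter.

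**4. With the plan's clustering.** Inputs from 8.1: mean volume 25 mm³; SD 10% to 20% of it, i.e. 2.5 to 5.0 mm³; two lesions per PAD patient with r = 0.5; 25 carotid and 10 PAD patients in phase two (25 + 2 × 10 = 45 lesions); 55 and 20 in phase one (55 + 2 × 20 = 95 lesions). Assumptions, because the documents are silent: the scanner splits, the SD ratio between scanners and a two-sided 0.05 level. The mean test allows for the lesion correlation. The SD ratio has a 95% bootstrap CI that resamples patients.

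| Patients (split) | SDs (mm³) | Mean test flags | SD-ratio CI excludes 1 |
|---|---|---|---|
| 35 (18/17) | 2.5 vs 5.0 | about 6% | about 85% |
| 35 (25/10, either way round) | 2.5 vs 5.0 | 1% to 14% | 62% to 92% |
| 75 (38/37) | 2.5 vs 5.0 | about 6% | about 99% |
| 35 (all splits) | 2.5 vs 3.75 | not tabulated | about 23% to 59% |
| 35 (all splits) | equal | not tabulated | 7% to 11% |

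All entries are simulation results and are rounded.

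**The case against.** Five points can be made for the plan.

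- *Extra scatter is not hidden.* The overall SD, the precision profile and the coverage probability in 8.1 would all worsen. With one scanner at twice the SD and an 18/17 split, the pooled SD is about 3.9 instead of 2.5 mm³. This stands, but nothing planned for Aim I volumes traces the loss to a scanner or site.
- *No pass/fail rule exists.* A reader might infer that a noisier scanner would pass, or that a non-significant F-test would be filed as proof of reproducibility. The documents do not support either. They give no acceptance limit and no 510(k) wording on reproducibility. The most that can be said is that this test would usually not flag it.
- *The gap is not general.* Aim II compares the individual equivalence criterion across institutions, scanner models and field strengths with bootstrap CIs. That criterion is built from squared differences and responds to scatter. The logistic models for degree and uniformity might respond too, but their outcome is not defined. The point is therefore limited to Aim I volumes.
- *Rescanning conflicts with the design.* Sections 2.3.1 and 5 promise no imaging beyond routine work-up, and the scan uses gadolinium. This stands, and it is why the fix asks for no rescans. The plan also says what it means by reproducibility: performance across sites, scanners and field strengths. Even on that meaning, a test of the mean covers only part of it.
- *The twofold ratio is a choice.* It joins the two ends of a planning range for one overall SD, and no document says that scanners differ this much. At a 1.5-fold ratio with 35 patients, the proposed SD comparison is itself weak.

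A reader might also assume that institution, scanner model and field strength coincide because there are two sites. The documents list no scanners, so this is only a possibility to check in the data.

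**Conclusion.** The point holds for Aim I volume measurements. Bias and overall precision against histology are estimated as planned. Scan-rescan variation cannot be separated from other error, and the analysis labelled reproducibility detects a difference in mean but not in spread. Under a twofold SD difference with equal means, the planned test flags about 6% of trials at near-equal splits (35 or 75 patients) and 1% to 14% at 25/10 splits. An SD comparison on the same data would usually detect the difference.

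These sizes rest on the assumed splits, SD ratio, normal errors and 0.05 level. The structural conclusion does not: it follows from one scheduled imaging visit and a regression on the signed difference.

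It would go too far to say that the study gives no information on consistency across sites and scanners. It tests consistency of mean bias, and Aim II has a comparison that responds to scatter.

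**What to change.** 1. In section 8.1, report the precision SD already defined there separately by institution, scanner model and field strength. Give SD ratios with bootstrap CIs that resample patients, beside the mean-bias tests. Present these as estimates with intervals and not as a pass/fail test: with equal SDs at n = 35 the interval excludes 1 in 7% to 11% of trials. Different patients sit under each condition, so a ratio away from 1 may partly reflect a different mix of plaques.
2. If the collected data show that institution, scanner model and field strength coincide, analyse one combined acquisition-configuration factor.
3. In objective I and its reporting, describe the result as consistency of bias and precision across acquisition configurations, and state that scan-rescan reproducibility was not assessed.

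The cost is a few more estimates from data already collected, imprecise at 35 patients, and a narrower claim. No further imaging or patients are required.
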